9.0 Procedures Involved

9.1 Study Design

This is a prospective multicenter randomized double arm study to evaluate the prevention of groin wound infections in patients undergoing vascular surgery which requires ≥ 8 cm groin incision.

9.11 Randomization Plan:

We will employ a 1:1 randomization to either Prevena or Dermabond using a stratified blocked randomization plan with strata determined as a single incision or a bilateral incision with sequences of random block sizes of 4 or 8. Within the bilateral incision strata, one incision will be randomly chosen relative to defining a single endpoint measure, with site of incision essentially serving as a secondary substratum.

9.12 Statistical Analysis Plan Outline:

Primary Endpoint

The primary endpoint for this trial will be Szilagyi wound infection grade quantified on an ordinal scale (none, grade I: infection contained to the dermus, grade II: infection extending into the subcutaneous tissue but the arterial graft is not involved, grade III: infection of the arterial graft or native vessel underlying the incision). The primary analysis will be intent to treat and carried forth using an ordinal regression model with a stratified likelihood accounting for the primary randomization strata (incision number) and binary indicator variable for treatment arm with the primary test of treatment efficacy being the proportional odds different from 1. In the event of sparse data at the higher grades of infection (<2% at grade III), categories II and III will be combined. For the bilateral incision strata, the primary endpoint will be determined by randomly choosing a single incision as determined within the randomization scheme.

Secondary Endpoint

The secondary endpoint will be a comparison of cost of treatment between the two arms and will be considered an exploratory analysis. We will utilize regression approaches to account for potential selection bias and censored cost endpoints. We have completed a preliminary appraisal of the additional per patient hospital costs (dispersed over the entire sample) for treating groin wound infections using the following assumptions. The associated wound infection rate for Prevena would be 6%.³ Groin wound infections for Prevena and Dermabond would require comparable care. Although lower wound severity grades have been reported for Prevena³ which could potentially decrease the complexity, duration and cost of subsequent treatment of wound infection for this group, the finding was not statistically significant.³ Therefore, we projected that treatment of groin wound infection in both groups would include an increased 10 day hospital length of stay,¹ seven days of IV antibiotics, daily CBC with or without differential and 2 cultures. We have estimated that the additional per patient cost of treating groin wounds if Prevena were used preemptively (\$935- \$1,114) would be similar to Dermabond (\$869- \$1,168) if the incidence of wound infection with Dermabond is $\leq 10\%$.

9.13 Sample size rationale:

Given $N=140=70+70$ total subjects and setting the Type I error rate = 0.05, we will have the power of 0.88 to detect a proportional odds of 4.9 different from 1. For our calculations, we assumed a probability vector for the ordinal scale (none, grade I, grade II, grade III) of (0.90, 0.08, 0.019, 0.001) for the Prevena treatment arm and (0.70, 0.16, 0.11, 0.03) for the Dermabond arm respectively. The power estimate was carried forth using 10,000 Monte Carlo simulations. This volume should be easily attainable over a 12 month period because on average 484 lower extremity revascularizations and 100 Abdominal Aortic Aneurysm Repairs are performed annually at Kaleida Health. While most of these procedures (85%) are completed by endovascular approach, access by groin cutdown is necessary in 25% of EVAR and 10% of EVI in addition to the planned open lower extremity revascularizations, which should allow for adequate numbers. SPSS 22 will be used to perform the statistical analysis.

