Clinical Protocol

NCT#02836990

Revised: August 11, 2017

Prevena Incision Management System Versus Dermabond in the Prevention of
Groin Wound Infections in Patients Undergoing Vascular Surgery

Principal Investigator: [name]
Department of Surgery
Buffalo General Medical Center
[contact]
[contact]

Sponsor: Acelity

Clinical Protocol Acceptance

I have read this protocol and agree to adhere to the requirements. I will provide copies of this protocol and all pertinent information to the study personnel. I will discuss this material with them and ensure that they are fully informed regarding the conduct of this study, other applicable regulations, to applicable laws and the University of Buffalo Health Science Institutional Review Board (HSIRB) requirements.

Principal Investigator Signature

____/____/____
DD MM YY

Principal Investigator Printed Name

Investigational Site

Protocol Synopsis

Prevena versus Dermabond in the Prevention of Groin Wound Infections in Patients Undergoing Vascular Surgery	
Protocol Number	
Test Device	Prevena Incision Management System
Primary Objective	To evaluate the clinical efficacy and cost effectiveness of Prevena versus Dermabond in preventing groin wound infections in patients who undergo vascular surgery requiring a groin incision.
Study Design	A prospective randomized study comparing groin wound infection rates and costs of hospitalization for Prevena and Dermabond in patients who undergo vascular surgery which requires a groin incision
Eligibility Criteria	Adults 18-85 who are scheduled to undergo vascular surgery which requires a groin incision who are able to consent and are willing to comply with follow-up and are or have a responsible individual deemed able to take care of a wound.
Number of Subjects	140 patients: 70 in each arm of the study
Number of Sites	Buffalo Medical Center, Kaleida Health
Follow-up schedule	Clinical follow-up will be daily throughout hospitalization including day of discharge and within 30 days of surgery to evaluate healing of the groin incision.
Primary Safety Endpoint	Major adverse event rate at 30 days defined as: groin wound infection
Primary Effectiveness Endpoint	30 day healing of the groin wound

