11.3 Securing the Data

The data will be collected by a single nurse coordinator with vascular surgery experience, who has received training on the case report forms developed for use in this study. The coordinator will also be trained to enter information from the case report form into a database set up in SPSS on a password protected PC kept in a locked office. All protected health information on the database will be de-identified. Subjects will be assigned a study number at time of randomization. The case report forms which contain patient identified protected health information will be kept in a locked cabinet within the coordinator's locked office. These will be retained for the required 3 year period following the study and then disposed of per institutional HIPPA policy. A master list of the patient name, DOB, hospital medical record number and study number to allow accurate linking of follow-up data to the index case will also be kept in a locked cabinet in the locked coordinator's office.

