19.3 Location of Research procedures

Research procedures will be completed in the following areas

- Surgeon's exam room, patient hospital room or other private room in the hospital
Patients may be screened for eligibility, consent obtained and randomized to a study arm in the surgeon's office, patient hospital room or other private room in the hospital.
- Operating Room

- Prevena (3 units) and Dermabond are both readily available in the OR supply area. The coordinator will ensure that there continues to be an adequate supply to allow for randomization. Both products are also used for other procedures, both vascular and other surgical interventions.
- The Clinical coordinator's office, participating surgeon's office, medical record department, hospital surgical unit
These areas may be used for collecting and in-putting data.

The aforementioned precautions will be used to assure patient confidentiality

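### The protocol discloses its block sizes (4 or 8) to recruiting staff in a trial with no described masking and no stated list concealment, so many assignments can be guessed in advance

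*Combined protocol and SAP*

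**What the plan says.** Sections 9.11 and 11.1 carry the same randomization text. Patients are allocated 1:1 to the two treatments from a blocked, stratified list, described as "strata determined as a single incision or a bilateral incision with sequences of random block sizes of 4 or 8". For bilateral patients one incision is chosen at random for the endpoint, "with site of incision essentially serving as a secondary substratum".

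On who sees this text, the Clinical Protocol Acceptance page has the investigator promise: "I will provide copies of this protocol and all pertinent information to the study personnel". Section 6.1 keeps the current version on site and expects the coordinator to know it well. Section 20.6 has the sponsor review it with each investigator and staff.

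On who recruits, sections 3.2 and 19.2 give candidate finding to the nurse coordinator. Section 28.0 lets the coordinator, a participating surgeon, a co-investigator or the principal investigator take consent. Section 19.3 says "Patients may be screened for eligibility, consent obtained and randomized to a study arm in the surgeon's office, patient hospital room" and makes the coordinator responsible for product supply. Section 11.3 adds: "The data will be collected by a single nurse coordinator with vascular surgery experience".

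The comparison is a portable negative-pressure device against a skin adhesive (section 9.4). The available text describes no masking, no holder of the allocation list, no central system and no envelopes. Three parts of the document were not available for this review, so this absence can be stated only for the rest.

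**The concern.** Random block sizes are meant to stop staff from working out the next assignment. That protection weakens when the sizes are printed in a document the recruiters hold and every past allocation is visible. Both sizes are also multiples of four, so a block can end only at the 4th, 8th, 12th patient of a stratum, and so on. A running tally is then enough to forecast many assignments before a patient is approached.

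The stated hypothesis (section 1.2) favours Prevena. Staff who expect a given arm next could, even without intent, approach or pass over a patient according to perceived wound risk. The arms would then differ at baseline. Intention to treat does not repair that, nor does a model stratified on incision number. The protocol mentions selection bias only for the exploratory cost analysis (section 9.12). With 70 patients per arm and assumed infection proportions of 10% and 30% (section 9.13), events are few and a handful of steered patients would count.

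**Working it through.** The plan states no predictability figure, so there is none to reproduce.

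**Inputs from the documents.** 1:1 allocation, block sizes 4 or 8, two strata (9.11); 140 patients in total (4.1).

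**Assumptions.** The probability q of drawing a 4-block is not given; q = 0.5 is the base case and is varied below. Stratum sizes are not given; 20 to 140 are used. The guesser knows all earlier allocations in the stratum and always names the arm that is behind.

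**Every fourth assignment, exact.**
1. If the position ends a block, the tally fixes the assignment: hit rate 1.
2. If it is the 4th place of an 8-block, the first three are all one arm with probability 2 × C(4,3)/C(8,3) = 8/56 = 1/7, and the lagging arm then has 4 of the 5 remaining places. Otherwise (6/7) it has 3 of 5. Hit rate = (1/7)(4/5) + (6/7)(3/5) = 22/35 = 0.629.
3. Mean block length in units of four is q + 2(1 − q) = 2 − q, so the long-run share of fourth positions that end a block is 1/(2 − q).
4. Long-run hit rate = 1/(2 − q) + [1 − 1/(2 − q)] × 22/35. At q = 0.5: 2/3 + (1/3)(22/35) = 0.876.

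For finite strata at q = 0.5 the average is 0.868 (20 patients), 0.872 (40), 0.874 (70) and 0.875 (140).

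| q (probability of a 4-block) | Long-run hit rate, every fourth assignment |
|---|---|
| 0 | 0.814 |
| 0.25 | 0.841 |
| 0.5 | 0.876 |
| 2/3 | 0.907 |
| 0.75 | 0.926 |
| 1 | 1.000 |

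**All assignments, simulation at q = 0.5** (10,000 sequences of 96). Hit rates at the 1st, 2nd, 3rd and 4th place of each four are 0.54, 0.65, 0.65 and 0.875. The mean is (0.5416 + 0.6492 + 0.6502 + 0.8752)/4 = 0.679. A Bayes-optimal guesser does no better (0.6785).

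**Confident forecasts, against sizes that are not all multiples of four.** Bayes guesser, strata of 35 and 105, all sizes in a set equally likely and known to the guesser:

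| | 4/8 | 6/8/10 |
|---|---|---|
| All assignments guessed right | 67–68% | 66% |
| Forecast with probability ≥ 75% | 38–40% | 26% |
| Certain | about 7% | about 2% |
| Right at every fourth assignment | 87% | about 72% |

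With 4/8, every fourth assignment falls in the ≥ 75% group, and forecasts in that group are right 87% of the time. Only about 16% of fourth assignments are fully determined.

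**The case against.** **The 87% describes the most predictable quarter of positions.** This stands. Over all assignments the rate is about 68%, and that figure belongs beside it.

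**A reader might infer that the multiples of four are the main fault and that new sizes cure it.** The arithmetic does not support that. Moving to 6/8/10 lowers the overall hit rate by only 1 to 2 points, and 4/6/8 leaves it at 67–68%. Most of the predictability comes from permuted blocks with known sizes and a visible history. New sizes mainly reduce the confident and certain forecasts.

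**A reader might infer a definite bias or type I error inflation.** No document supports a number. In an illustration with no true effect and 20% infection, recruiters act only on forecasts of at least 75% and shift patient risk by 10 points. That gives a spurious difference of 2.9 points with 4/8 and 1.7 with 6/8/10. If they act on any forecast above 50%, it is 3.4 against 3.5. The type I errors in the first case (0.06 against 0.056) do not differ beyond simulation error. The risk shift is invented, and the illustration used a simple two-proportion test rather than the planned ordinal model.

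**Existing safeguards.** Section 3.2 has all referrals monitored and eligible patients approached, section 23.2 logs screen failures with reasons, and section 19.3 lists consent before randomization. These make passing over patients more visible, but they do not conceal the next assignment. The three-day contact in section 28.0 is for patients who are undecided and gives staff no discretion over timing.

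**Who knows the history.** That one coordinator sees every allocation is an inference. Section 20.3 also gives screening and data collection to a research assistant, there are two sites (19.1), and the substratum for bilateral patients could split the tally. If it has its own blocks, the same calculation applies within each.

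**Concealment may exist** in the parts not available. If so, the block sizes are still disclosed.

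**Conclusion.** The concern holds as a weakness that is cheap to remove. The plan tells recruiting staff the block sizes, and the available text does not say how the list is concealed. That the trial is open is inferred from the visibly different treatments and the lack of any described masking.

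The predictability figures (about 68% overall, about 87% at every fourth assignment, about 40% forecast with at least 75% probability, about 7% certain) assume equally likely block sizes and full knowledge of past allocations in the stratum. Under any mix of 4 and 8 the long-run rate at every fourth assignment is at least 81%. A guesser with partial knowledge would do worse.

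The documents do not show that any selection has taken place, and the size of a resulting bias cannot be derived from them. The point is that the design permits such selection and the planned analysis could not remove it.

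**What to change.** 1. Delete the block sizes from sections 9.11 and 11.1. Say only that permuted blocks of varying, undisclosed size are used, and keep the sizes in a restricted document.
2. Have the trial's existing biostatistician generate and hold the list, outside recruitment. If a concealment procedure already exists, state it.
3. Release each assignment singly (by telephone, locked electronic list or opaque numbered envelope), only after consent and stratum have been logged.
4. As a secondary step, draw a new list for the remaining patients with sizes that are not all multiples of four, for example 6, 8 and 10. If those sizes became known, confident forecasts would fall to about 26% and certain ones to about 2%, but the overall hit rate only to about 66%.

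The cost is a one-paragraph amendment, a little of the 10–20 biostatistical hours in section 20.3, and a call or envelope for each patient. With 6/8/10 the largest possible arm imbalance within a stratum rises from 4 to 5 (half the largest block). Patients already randomized gain nothing. How many remain is unclear: the revision is dated August 2017, while section 7.3 projected completion by 05/31/17. Sample size, endpoint and analysis are unchanged.

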9.2 Research Procedures

- Baseline Requirements
 - Informed consent must be obtained from the subject prior to enrollment. The following is a list of all assessments and tests that are required during the baseline period. Assessment is based on data available to the investigator at time of enrollment.
 - Medical History- It is required that the subject's clinical history and pre-existing conditions be assessed and documented
 - Physical Exam- It is required that the subject undergo a pertinent arterial and venous physical exam and the results be documented
 - Concomitant Medication use- It is required that the subject's use of medications related to the study be provided and documented at baseline and throughout follow-up. Concomitant use includes antibiotics, NSAIDs, steroids, aspirin, anticoagulants and antiplatelet medications
 - Laboratory Testing- Routine laboratory testing performed prior to a surgical procedure will be documented: CBC without Differential, Electrolyte Panel
- Procedure Requirements
 - Concomitant Medication Use
 - Adverse Event (AE) evaluation- any undesirable medical occurrences in a subject related or unrelated to the study device, study procedure or study requirements that is identified or worsens during the clinical study. Adverse events must be assessed and documented by the investigator at the time of the procedure and at all follow-

ups (scheduled and unscheduled visits). All suspected AEs must be recorded and reported to the sponsor. See 12.0 **Data Safety Monitoring** for definitions of specific AEs and AE categorization.

- Post Procedure Requirements
 - Clinical Status Evaluation :
 - Sizalgyi Infection Score
 - Grade 0- No Infection
 - Grade I- Dermis only
 - Grade II- Subcutaneous tissue involvement
 - Grade III- Arterial Graft Involved
 - Lower extremity vascular assessment
 - Documentation of pulses, color, movement
 - Sensation, Ankle Brachial Index (ABI)
 - Concomitant Medical Use: Prophylactic antibiotics will be noted. Use of additional antibiotics along with indication will be recorded. Other medications such as NSAIDs, steroids, aspirin, anticoagulants and antiplatelet medications will also be recorded.
 - AE Evaluation: any infection of the randomized incision or other major postoperative morbidity related or unrelated to the surgical procedure/ wound treatment which may include but is not limited to: MI, CHF, CVA, Respiratory distress/failure, renal failure requiring dialysis, re-intervention for any reason, thrombosis, embolization, amputation, blood loss requiring treatment.

Table1. Study Assessment Requirements

Assessment Schedule (Time-Frame Window)	Baseline ≤45 days prior Labs ≤ 30 days prior	Procedure	Daily While Hospitalized	Day of Discharge	30 Day Follow-up 25-40 Days
Medical History	X				
Physical Exam	X				
Concomitant Medication Use	X	X	X	X	X
Laboratory Testing	X				
Clinical Status Evaluation	X	X	X	X	X
With ABI	X		X _(x1)	X	X
Adverse Event Evaluation		X	X	X	X

9.3 Procedures to lessen the probability or magnitude of risks

- The randomized surgical incision will be irrigated copiously with a solution of saline and antibiotics
- Subjects and caretakers will be educated on the signs and symptoms of infection/allergic reaction, use of the Prevena.

9.4 Device description, purpose and regulatory approval status

Prevena Incision Management System by Acelity

Prevena is a negative pressure wound therapy device intended for use on surgical incisions that continue to drain following closure with either staples or sutures. Prevena promotes healing by maintaining a closed environment which protects the incision from external infectious sources. Through the application of negative pressure, Prevena removes fluids, and potentially infectious exudate from the surgical site. Prevena is lightweight and portable.

Dermabond

Dermabond by Ethicon is a cyanoacrylate adhesive that forms bonds across wound edges to promote healing. When Dermabond comes in contact with moisture on the skin surface, it binds to the top epithelial layer and bridges the edges of the incision together, allowing healing to occur beneath. It has been marketed to replace sutures ≤ 5.0 in diameter for repair of lacerations or incisions. The multiple benefits of Dermabond include an antimicrobial water resistant coating that protects against external sources of infection, application time is shorter than suture placement, need for suture removal is eliminated and long term cosmetic outcomes are comparable. When Dermabond is used in the extremity or torso, placement of subcutaneous sutures is usually recommended as this tends to improve healing. When used in moist areas of high tension or mobility such as the groin, the incision must be kept dry and mobility restricted.¹⁵

9.5 Source Records and Data Collection Sheets

Source records will include the subjects hospital electronic/paper medical and financial records, surgeons office records and home health care records.

Data collection sheets will include patient demographics, co-morbidities, available preoperative vascular testing, operative data, operative, postoperative complications, reintervention, clinical assessment as per table II, antibiotic use and other concomitant medications, hospital LOS, 30 day hospital readmission for infection, total, direct and indirect hospital costs, reimbursement, contribution margin, discharge and 30 day (25-40) clinical assessment (see table II) antibiotic use, use of home health services for wound assessment/care of the randomized incision, or unscheduled office appointments for evaluation or treatment of the randomized incision.

9.6 Data/Long term Follow-up

Patients will be assessed at 30 days (25 -40) following vascular surgery with groin

incision to evaluate healing.

10.0 Data Banking

10.1 Data will not be stored for future use

11.0 Data Management

11.1 Data analysis plan and 11.2 Power Analysis

Study Design

This is a prospective multicenter randomized double arm study to evaluate the prevention of groin wound infections in patients undergoing vascular surgery which requires ≥ 8 cm groin incision.

Randomization Plan:

We will employ a 1:1 randomization to either Prevena or Dermabond using a stratified blocked randomization plan with strata determined as a single incision or a bilateral incision with sequences of random block sizes of 4 or 8. Within the bilateral incision strata, one incision will be randomly chosen relative to defining a single endpoint measure, with site of incision essentially serving as a secondary substratum.

Statistical Analysis Plan Outline:

Primary Endpoint

The primary endpoint for this trial will be Szilagyi wound infection grade quantified on an ordinal scale (none, grade I, grade II, grade III). The primary analysis will be intent to treat and carried forth using an ordinal regression model with a stratified likelihood accounting for the primary randomization strata (incision number) and binary indicator variable for treatment arm with the primary test of treatment efficacy being the proportional odds different from 1. In the event of sparse data at the higher grades of infection (<2% at grade III), categories II and III will be combined. For the bilateral incision strata, the primary endpoint will be determined by randomly choosing a single incision as determined within the randomization scheme.

Secondary Endpoint

The secondary endpoint will be a comparison of cost of treatment between the two arms and will be considered an exploratory analysis. We will utilize regression approaches to account for potential selection bias and censored cost endpoints. We have completed a preliminary appraisal of the additional per patient hospital costs (dispersed over the entire sample) for treating groin wound infections using the following assumptions. The associated wound infection rate for Prevena would be 6%.³ Groin wound infections for Prevena and Dermabond would require comparable care. Although lower wound severity grades have been reported for Prevena³ which could potentially decrease the complexity, duration and cost of subsequent treatment of wound infection for this group, the finding was not statistically significant.³ Therefore, we projected that treatment of groin wound

infection in both groups would include an increased 10 day hospital length of stay,¹ seven days of IV antibiotics, daily CBC with or without differential and 2 cultures. We have estimated that the additional per patient cost of treating groin wounds if Prevena were used preemptively (\$935- \$1,114) would be similar to Dermabond (\$869- \$1,168) if the incidence of wound infection with Dermabond is $\leq 10\%$.

Sample size rationale:

Given $N=140=70+70$ total subjects and setting the Type I error rate = 0.05, we will have the power of 0.88 to detect a proportional odds of 4.9 different from 1. For our calculations, we assumed a probability vector for the ordinal scale (none, grade I, grade II, grade III) of (0.90, 0.08, 0.019, 0.001) for the Prevena treatment arm and (0.70, 0.16, 0.11, 0.03) for the Dermabond arm respectively. The power estimate was carried forth using 10,000 Monte Carlo simulations. This volume should be easily attainable over a 12 month period because on average 484 lower extremity revascularizations and 100 Abdominal Aortic Aneurysm Repairs are performed annually at Kaleida Health. While most of these procedures (85%) are completed by endovascular approach, access by groin cutdown is necessary in 25% of EVAR and 10% of EVI, which should allow for adequate numbers. SPSS 22 will be used to perform the statistical analysis.

